8.1 Liver histopathology and immunohistochemistry

8.1.1 Liver histopathology

One liver histopathologist (RP) with specific expertise in NAFLD, blinded to the clinical, laboratory and study treatment allocation, will perform all the histopathological assessments at the central trial site (HUMANITAS Gradenigo) using an in-house designed proforma. The histological diagnosis of NASH will be established using H&E staining and haematoxylin van Gieson stains of formalin-fixed paraffin-embedded liver tissue. Both the baseline and end-of-treatment (72 weeks) biopsies will be reported as either 'definite NASH,' 'uncertain NASH' or 'not NASH.' The histological diagnosis of 'definite NASH' is defined as a combination of >5% macrovesicular steatosis, hepatocyte ballooning (\pm Mallory's Hyaline) and lobular inflammation (mixed infiltrate, related to foci of ballooning)⁴⁶. The assessment of ballooning is subjective, and thus for 'uncertain' hepatocyte ballooning, a key component of the diagnosis of NASH, ubiquitin immunohistochemistry will be used to identify material compatible with Mallory's hyaline.

To validate the quality of the biopsy specimen, the core specimen length will be measured and the number of portal tracts will be recorded.

The NAS will be calculated based on the Kleiner classification⁴⁷ The NAS is scored of 8, with 8 representing the highest activity. The NAS is the sum of scores of the 3 components of the histological scoring system, namely steatosis (0= \leq 5%, 1=5–33%, 2= \geq 33–66%, 3= \geq 66%), lobular inflammation (0=no foci, 1= \leq 2 foci/ \times 200, 2=2–4 foci/ \times 200, 3= \geq 4 foci) and hepatocyte ballooning (0=none, 1=few ballooned cells, 2=many cells/prominent ballooning). The Kleiner scoring system for NAFLD fibrosis (F0-F4) will be used to evaluate the stage of fibrosis in each biopsy specimen. Portal tract changes (inflammation, interface hepatitis, ductular reaction), an intrinsic feature of NASH, will also be recorded⁴⁸. The pathologists will score each histological feature of liver biopsies and fill in separate forms.

8.1.2 Potential relevance of Nuclear Factor κ B (NF- κ B) activation in the liver and mononuclear cells (MNCs) for NASH pathogenesis and curcumin treatment

The pro-inflammatory transcription factor **Nuclear Factor(NF)- κ B** is a master regulator at the crossroads of metabolic, oxidative, immune and inflammatory pathways and a known molecular target of curcumin(3,49). NF- κ B activation in all liver cell subtypes and in peripheral mononuclear cells (MNCs) plays a central role in NASH pathogenesis and progression and in NAFLD-associated metabolic abnormalities((⁵⁰, ⁵¹, ⁵²,⁵³, ⁵⁴). We therefore assessed the effect of treatment on NF- κ B activation in the liver and in circulating MNCs.

Nuclear Factor(NF)- κ B activation in the liver by immunohistochemistry

The ImmunoCruz® Staining System will be used in deparaffinized liver tissue according to the manufacturer's instructions (Santa Cruz Biotechnology, Santa Cruz, CA). Briefly, slides will be soaked in 3% hydrogen peroxide for 5 min, washed, and incubated in serum blocking solution for 20 min. Specimens will be then incubated with primary antibodies for 2 h at 37° C. Tissue samples will be probed with mouse monoclonal antibodies reactive to NF- κ B p65 (Santa Cruz Biotechnology). After rinsing, specimens will be incubated with biotinylated secondary antibody and a horseradish peroxidase-streptavidin complex, for 30 min each. Tissue samples will be then colorized with DAB substrate, counterstained, mounted, and examined. NF- κ B immunoreactivity will be expressed as the % of positive cells/high-power field ($\times 400$)⁵⁵ and will also be semiquantitatively evaluated using a 4-point scoring system (0—no staining; 1—positive staining in <30% of cells/high-power field; 2— positive staining in 30–70% of cells/high-power field; 3—positive staining in >70% of cells/high-power field).

NF- κ B activation in circulating mononuclear cells(MNCs).

Blood samples were collected in tubes containing Na-EDTA as an anticoagulant; 3.5 mL of the anticoagulated blood sample was carefully layered over 3.5 mL of the PMNL isolation medium (Robbins Scientific Corp, Sunnyvale, CA). Samples were centrifuged at 450 x g in a swing outrotor for 30 min at 22 °C. At the end of centrifugation, 2 bands separate out at the top of the red blood cell pellet. The top band consists of mononuclear leukocytes(MNCs), whereas the bottom band consists of polymorphonuclear leukocytes(PMNs). The MNC and PMN bands were harvested with a Pasteur pipette, repeatedly washed

with Hank's balanced salt solution, and reconstituted to a concentration of 4×10^5 cells/mL in Hank's balanced salt solution. This method yields > 95% pure PMN and MNC suspensions(56).

NF-kBp50/p65 transcription factor assay kit was purchased from Cayman Chemical (Ann Arbor MI, USA). The method detects specific transcription factor DNA binding activity in nuclear extracts and cell lysates. A specific double stranded DNA sequence containing the NF-kB response element is immobilized onto the bottom of wells of a 96 well-plate. NF-kB in nuclear or cytoplasmatic extract binds specifically to the NF-kB response element. NF-kBp50/65 is detected by addition of specific primary antibody directed against NF-kBp50/65. A secondary antibody conjugated to Horseradish peroxidase is added to provide a sensitive colorimetric readout at 450 nm.

Other clinical and laboratory data

Fasting blood samples will be analysed for full blood count, urea, creatinine and electrolytes, thyroid stimulating hormone (TSH), lipid profile (total cholesterol, high density lipoprotein, triglycerides), liver function tests, prothrombin time, international normalised ratio (INR), amylase, α -fetoprotein, C reactive protein, HbA1c, Monocyte chemoattractant protein-1(MCP-1), and plasma glucose using standard laboratory methods (Roche Modular system, Roche Ltd, Lewes, UK). Urinary albumin excretion rate will be measured using standard routine methods.

Serum Insulin (Merckodia, Uppsala, Sweden), nonesterified fatty acids (Zen-Bio, Research Triangle Park, North Carolina, USA) and CK-18 M30 (M30 Apoptosense ELISA Kit; PEVIVA AB, Bromma, Sweden) lumican and adiponectin will be measured in-house using commercially available colorimetric ELISAs.

Serum caspase-cleaved cytokeratin-18 (CK-18 M30) was performed at study entry to assess hepatic apoptosis. HOMA-IR, a marker of insulin resistance, was calculated in the standard fashion: $\text{glucose} \times \text{insulin} / 22.5$. Measurements of weight (kg), height, systolic/diastolic blood pressure and waist:hip circumferences were recorded. Waist and hip circumferences were defined as

the circumferential measurements immediately above the level of the iliac crests and at the level of the greater trochanters, respectively. BMI was defined as weight in kilograms divided by the square of the height in metres (kg/m²).

Nuclear Factor(NF)- κ B activation in mononuclear cells (MNCs)

Blood samples will be collected in tubes containing Na-EDTA as an anticoagulant; 3.5 mL of the anticoagulated blood sample will be layered over 3.5 mL of the PMNL isolation medium (Robbins Scientific Corp, Sunnyvale, CA). Samples will be centrifuged at 450 x g in a swing outrotor for 30 min at 22 °C. At the end of centrifugation, 2 bands separate out at the top of the red blood cell pellet. The top band consists of mononuclear leukocytes(MNCs), whereas the bottom band consists of polymorphonuclear leukocytes(PMNs). The MNC and PMN bands will be harvested with a Pasteur pipette, repeatedly washed with Hank's balanced salt solution, and reconstituted to a concentration of 4 x 10⁵ cells/mL in Hank's balanced salt solution. This method yields > 95% pure PMN and MNC suspensions(57).

NF-kBp50/p65 transcription factor assay kit was purchased from Cayman Chemical (Ann Arbor MI, USA). The method detects specific transcription factor DNA binding activity in nuclear extracts and cell lysates. A specific double stranded DNA sequence containing the NF-kB response element is immobilized onto the bottom of wells of a 96 well-plate. NF-kB in nuclear or cytoplasmatic extract binds specifically to the NF-kB response element. NF-kBp50/65 is detected by addition of specific primary antibody directed against NF-kBp50/65. A secondary antibody conjugated to Horseradish peroxidase is added to provide a sensitive colorimetric readout at 450 nm.

Determination of plasma curcumin and curcumin metabolites

We used a validated HPLC-MS/MS method to simultaneously measure plasma curcumin, demethoxycurcumin, bis-demethoxycurcumin, tetrahydrocurcumin and octahydrocurcumin blood samples of all included patients during the oral fat tolerance test and of the oral glucose tolerance test^{58, 59, 60}.

To investigate curcumin and curcumin metabolite kinetics after coingestion with fat or glucose, on the day of the oral tolerance tests patients took two pills of their curcumin/placebo formulations together with the glucose or fat meal, and blood samples were subsequently drawn at the predefined times (see below)

Dietary and physical activity record

Dietary record with food frequency questionnaire. Subjects will be instructed to fill in a 7-day validated and reproducible dietary questionnaire during an individual training session with a nutritionist; a list of foods is designed, for each item different portion sizes are specified according to the EPIC study⁽⁶¹⁾. The diet record was analyzed using the WinFood database (Medimatica, Teramo, Italy) according to the table of food consumption of the Italian National Institute of Nutrition and Food Composition Database for Epidemiological Study in Italy⁽⁶²⁾. Based on FFQ data, excessive alcohol use will be defined as .30 g/d for male individuals and .20 g/d for female individuals.

The FFQ will be completed at baseline (visit 1) and at end-of-treatment (visit 7). Analysis will report the change from baseline scores to the end-of-treatment .

Physical activity record.

Physical activity (PA) will be measured with the accelerometer SenseWear Armband (SWA), which had to be worn continuously on the nondominant arm for at least 3 consecutive days (2 working days and a weekend day) at baseline and at EOT. The SenseWear Armband (SWA) is a relatively new accelerometer device that can be used to quantify and monitor physical activity and energy expenditure (EE), which has been validated against indirect calorimetry⁶³ and has been shown to have acceptable reliability and reproducibility. The SWA is designed to be worn on the upper arm over the triceps. Its internal sensors include an accelerometer, a thermal flow sensor, a galvanic sensor that records skin response, a skin temperature sensor, and an air temperature sensor. The accelerometer in the armband has two axes and uses a microelectromechanical sensor that measures movement.

Physical activity is measured relative to gravity ($1\text{ mg}=9.81\text{ mm/sec}^2$) with an interval of 20 ms and categorized based on intensity, according to White et al.⁶⁴, into time spent in sedentary behavior (48 mg) and in light (48–154 mg, e.g., walking), moderate (154–389 mg, e.g., cycling), and vigorous activities (.389 mg e.g., running). The software created by the manufacturer calculates then EE using a patented algorithm that combines acceleration, heat flow, and other parameters: technical and statistical procedures have been described in detail earlier^{65, 66, 67}.

PA record will be completed at baseline (visit 1) and at end-of-treatment (visit 7). Analysis will report the change from baseline scores to the end-of-treatment .

Upper abdomen ultrasound and computerized sonographic hepato-renal ratio for quantification of steatosis

All examinations will be performed at each patient visit with a GE Vivid7 ultrasound machine (GE Healthcare, Horten, Norway) equipped with a GE 4C curved array transducer (GE H4904PC). US studies will be performed by two experienced radiologists (GM and EP) who were unaware of the patient's clinical details and laboratory findings. All the instrument settings, including "gain," "depth," and "time-gain compensation," will be preset and fixed for each measurement. For assessment of US H/R ratio, ultrasound images with both liver and right kidney clearly visualized will be obtained in the sagittal liver/right kidney view in the lateral position. US hepatic echo-intensity attenuation rate was assessed in right intercostals view at anterior axilla line in the supine position. All images will be reviewed by one of the two radiologists involved in scanning. Analysis of digitized ultrasound images was performed by using NIHimage software (ImageJ 1.41o, National Institutes of Health, Bethesda, MD).

US hepatic/renal echo-intensity ratio

In sagittal liver/right kidney view, a region of interest (ROI) of $1.5 \times 1.5\text{ cm}$ (1,296 pixels) in the liver parenchyma was selected. This area is large enough to calculate an average histogram value and small enough to avoid the inclusion of vessels or bile ducts in the specimen. Several ROI parameters were displayed including circumference and area, total brightness level, mean brightness level, SD, most frequent

brightness level, and a histogram. Of all these

parameters, we used only the mean brightness level for each organ (liver and right kidney) in this study.

Technically, the echo intensity can be influenced by many factors, particularly by gain intensity.

To avoid confounding by factors that can modify the echo intensity and thus bias comparisons,

the mean brightness levels of both the liver and the right kidney cortex were obtained on the

same longitudinal sonographic plane. The ratio between the mean brightness level of the liver and the right

kidney was calculated manually to determine the hepatorenal sonographic index.

In each case, the calculation of the hepatorenal sonographic index was repeated at least twice.

When the difference was less than 0.20, the average was calculated. If there was a greater discrepancy, a

third measure was performed and the average of the two closest measurements was used.

The ROI had to be as uniform as possible, excluding blood vessels, bile ducts, and other focal

hypo/hyperechogenicity. Another ROI of 0.5×0.5 cm (144 pixels) was identified in the right renal cortex

with no large vessels, renal sinus or medulla. To avoid the interference of depth-dependent echo-intensity

attenuation and the borderline echo distorting effects, the boundary between liver and right kidney area

should be placed near the center of the image, and the liver and right kidney ROIs were selected at the same

depth of the ultrasound images. The gray scale mean value of the mixels within the two ROIs was used as

measurement of echo intensity. Then we divided the average hepatic gray scale by the average renal cortex

gray scale to calculate the US hepatic/renal ratio. US hepatic echo-intensity attenuation rate

In right intercostals view at anterior axilla line, a tangent line of the sector ultrasound image was drawn and

the ultrasound wave transmission line was determined, starting from the point of tangency and perpendicular

to the tangent line. Two ROIs of 1.5×1.5 cm (1,296 pixels) were selected in liver homogeneous regions

along the ultrasound transmission line near the liver anterior margin (depth 4–6 cm) and the liver posterior

margin, respectively. The linear distance

between the two ROIs was also measured.

The echo intensity of ultrasound wave was attenuated exponentially, shown as the following equation:

$$A = A_0 e^{-\alpha d}$$

$$d = 0 \times e^{-\alpha d} \quad (1)$$

Where A_0 and A_d are ultrasound echo intensity at the sound source and the liver parenchyma at a specific

depth, respectively; a is the attenuation coefficient of the liver parenchyma; f is the frequency of the ultrasound detector; d is the depth of ROI. The ratio of the average echo intensity in the liver near-field ROI to liver far-field ROI was then calculated based on equation (1):

$$\frac{A_n}{A_f} = e^{-2a(d_n - d_f)} \quad (2)$$

Where A_n and A_f are average ultrasound echo intensity in the near-field ROI and the far-field ROI, respectively; a and f have been defined in equation (1); d_n and d_f are the depth of liver near-field and far-field ROIs.

8.4 Metabolic substudy

ORAL FAT TOLERANCE TEST(OFTT). Within 3 months from entry, all patients will undergo a standard oral fat load test.

Participants will be encouraged to avoid strenuous physical efforts and to follow their usual diet during the 24 hours preceding the test. The fat load consists of a mixture of 200 ml dairy cream (35% fat) and 26 g egg yolk for a total energy content of 766 kcal.: 78.3 g fat (55.6% saturated fatty acids, 29.6% monounsaturated fatty acids, 14.8% polyunsaturated fatty acids), 595 mg cholesterol, 8.8 g protein, 7 g carbohydrate. The fat load will be consumed over 5 minutes; subjects will be kept fasting on the test morning, and strenuous activity will be forbidden.

Samples will be drawn at 0 (baseline), 2, 4, 6, and 8 hours. Plasma total cholesterol (Chol), triglyceride (Tg), and free fatty acids (FFA) will be measured by automated enzymatic methods. Very low-density lipoproteins (VLDL) will be isolated through preparative ultracentrifugation and assayed for their Tg and total Chol content. Apo E genotype will be determined by polymerase chain reaction amplification of genomic DNA using specific oligonucleotide primers.

Separation of Triglyceride-Rich Lipoprotein Subfractions.

Very-low-density lipoproteins (VLDL) will be isolated through preparative ultracentrifugation and subsequently assayed for their Tg and total Chol content. One aliquot plasma will be brought to densities of 1,006 g/l by adding a KBr solution ($d_{1,330}$ g/l) and centrifuged at 105,000g for 21 hours at 10°C in a Beckman L8-70M ultracentrifuge. Tg and total Chol concentration will be then determined in lipoprotein fraction enzymatically. The first higher amount of blood (10 ml) will be drawn for subfractionating triglyceride-rich lipoprotein (TRLPs) by ultracentrifugation on a discontinuous density gradient. Separated plasma will be brought to a density of 1.10 g/ml by adding solid KBr. The density gradient will be prepared by adding to 4 ml of this plasma 3 ml of a 1.065 g/ml solution containing 0.05% KBr/NaCl plus EDTA (pH 7.4); 3 ml of a similar solution at 1.020 g/ml; 3 ml of physiological saline at 1.006 g/ml. The sample will be ultracentrifuged in a Beckman L8-70M centrifuge at 20°C in stages, allowing the separation of four VLDL fractions with decreasing Sf values: A₄₀₀; B₁₇₅₋₄₀₀; C₁₀₀₋₁₇₅; D₂₀₋₁₀₀. The first centrifugation (28,300 rpm for 43 minutes) isolates fraction A in a floating volume of 0.5 ml. The volume removed will be replaced with physiological saline, and the sample centrifuged at 40,000 rpm for 67 minutes to isolate fraction B. This procedure will be then repeated at 40,000 rpm for 71 minutes and at 37,000 rpm for 18 hours to isolate fractions C and D, respectively.

The automated methods mentioned will be used to determine Chol and Tg on the 4 fractions.

ApoB48 and ApoB100 Analysis. TRLP ApoB48 and ApoB100 will be separated by sodium dodecyl sulfate polyacrylamide gel electrophoresis (SDS-PAGE) using 3.9% gel. Nondelipidated samples will be reduced in SDS buffer for 4 minutes at 96°C. Samples will be applied to the gel and run at 40 mA in 0.025M Tris, 0.192M glycine, and 0.1% SDS. Gel will be stained with Silver Stain (Bio-Rad). Because the chromogenicity of ApoB48 is similar to that of ApoB100, a protein standard was prepared from LDL isolated by sequential ultracentrifugation and used to quantify ApoB100 and ApoB48. The bands were quantified by densitometry using Gel Doc equipment (Bio-Rad). Density values were assigned to the ApoB100 bands of the standard LDL, and a standard curve will be constructed. The values will be recalculated by linear regression.

Oxidized LDLs measurement. LDL-conjugated dienes will be determined during the fat load test, as follows. Capillary electrophoresis will be performed as described by Stocks and Miller. The cathode and anode electrolytes and the capillary run buffer will be 40 mM methylglucamine-Tricine, pH 9.0. LDL samples will be injected by low pressure for 4 seconds. Dimethylformamide will be injected as an electroosmotic flow marker for 1 second. A voltage of 24 kV was applied ramping over 0.8 minutes. Migration of LDL particles will be monitored at 200 and 234 nm. The amount of conjugated dienes will be obtained from the percentage of the height of LDL peak at 234 nm related to the height of LDL peak at 200 nm.

ORAL GLUCOSE TOLERANCE TEST (OGTT). Within 3 months from entry into the trial, patients will undergo a standard 75-g oral-glucose-tolerance test (OGTT), with measurement of plasma glucose, insulin, C-peptide, FFA. Areas under the concentration curves (AUCs) of different parameters during the OGTT will be calculated with the trapezoidal method.

The following parameters will be calculated:

Whole body insulin sensitivity. Prehepatic insulin delivery will be estimated as the suprabasal (D) 30-min AUC of C-peptide divided by the 30-min increase in plasma glucose. The hepatic insulin extraction, as a percentage of secreted hormone, will be estimated by $[1 - \frac{\text{AUC insulin}}{\text{AUC C-peptide}}]$. Two indexes of insulin sensitivity will be calculated: the conventional quantitative insulin-sensitivity check index (QUICKI) and oral glucose insulin sensitivity (OGIS), an OGTT-derived index of whole-body insulin sensitivity⁶⁸.

Adipose tissue insulin resistance. Adipose tissue insulin resistance will be calculated (adipose IR = fasting FFA x fasting plasma insulin), as previously described and validated in diabetic and nondiabetic subjects⁶⁹.

70.

Hepatic and muscle insulin resistance. The hepatic and muscle insulin resistance index will be calculated from OGTT as proposed and validated against clamp in nondiabetic subjects⁷¹

Hepatic insulin extraction. The hepatic insulin extraction (He), as a percentage of secreted hormone, will be estimated using the formula $[1-(\text{AUC insulin}/\text{AUC C-pep})]$.

Pancreatic β -cell function. Two OGTT-derived indexes of β -cell function will be calculated⁷²: the insulinogenic index (IGI), computed as the suprabasal serum insulin increment divided by the corresponding plasma glucose increment in the first 30 min (DI30/DG30), and the C-peptide–genic index, computed as DC-peptide30/DG30, which were previously validated against measures of β -cell functions derived from the frequently sampled intravenous glucose tolerance test (FIVGTT). The ability of β -cell to adapt insulin secretion to changes in insulin sensitivity will be assessed by 2 indexes, the disposition index and the adaptation index, which are calculated by multiplying OGIS times IGI and C-peptide–genic index values, respectively. These indexes relate β -cell insulin secretion to insulin resistance and represent integrated parameters of β -cell function, validated against FIVGTT minimal model variables in NAFLD subjects^{73, 74}; they also accurately predict future type 2 diabetes in the general population^{75, 76}.

9. Statistical analyses

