5.1 Eligibility criteria

Eligible adult patients (≥ 18 years old) were identified and recruited at the participating trial site centres starting in August 2018 and ending by June 2022, 52 patients will be recruited. Participating trial centres will include the Liver and Metabolic Units at the Humanitas Gradenigo Hospital (Turin) since August 2018), and the Metabolic Unit of Dept of Medical Sciences at the Città della Salute e della Scienza hospital (Turin) since Sept 2018).

All trial participants will give informed written consent at the beginning of the screening visit prior to undergoing any tests and procedures needed to assess eligibility.

Eligibility for the trial will be determined at screening visit 1 by standard blood tests, clinical history (including written-confirmation of drug history where necessary) and physical examination to identify other illnesses or contraindications for participation.

Patients who satisfied the eligibility criteria trial at both sites will be offered to take part in a metabolic mechanistic substudy. The substudy involves a standard Oral Glucose tolerance Test (OGTT) and a standard Oral Fat Tolerance Test (OFTT) on three admissions (at least 24 hours apart from each other) and an indirect calorimetry test at the two participating centres on visits 2 (pretreatment) and 8 (4 weeks

post-treatment). A detailed summary of the metabolic substudy will be published separately. A patient's decision to partake or withdraw from the metabolic substudy will not affect their participation in the main 72-week trial.

A schematic view of trial schedule and design is presented in **Figure 1**.

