Both active treatment (phytosomal curcumin) and placebo control will be packaged and labelled with a unique identification number (in keeping with the European Unions Good Manufacturing Practice for Medicinal Product guidelines) by the manufacturer (Indena S.p.A.), to the extent that the receiving trial site will be blinded to the study drug throughout the duration of the trial. Sealed parcels (containing electronic information) will be sent with each drug package for the attention of the unblinded members of the central trial management group (TMG) nominated statistician, RG and database programmer, EP, to ensure (1) safe delivery of the correct drug and (2) blinding of the treatment allocation from the remainder of the TMG and the trial patient. Unblinding of treatment will only take place if the identity of the allocated study medication will be necessary for patient safety and care. If a serious adverse event (SAE) is deemed unexpected and possibly, probably or definitely related to phytosomal curcumin (ie, suspected unexpected serious adverse reaction=SUSAR), a clinical member of the TMG was unblinded to the medication to evaluate causality and subsequently label the event either as an unrelated SAE (for patients receiving placebo) or a SUSAR (for patients receiving phytosomal curcumin). The latter will be reported to the MHRA and the NRES, and only if patient safety is jeopardised the study medication will be discontinued and the treating clinician/patient informed.

6. Trial schedule and data collection

The trial will involve nine patient-related visits at their nearest trial site (**Figure 1**).

The study comprises four stages: (1) screening, enrollment, randomisation and baseline investigations (visits 1 and 2, over a maximum period of 14 days), (2) 504 days of study treatment (visits 3–7, over 72 weeks), (3) primary endpoint assessment including liver biopsy (visit 8, within 1 day of the EOT) and (4) post-treatment follow-up assessment (visit 9, 12 weeks after EOT). If the trial investigating team or the trial participant suspected an AE, an unscheduled visit was arranged within 24 h. Each visit included patient interview, clinical examination, anthropometry and blood/urine chemistry.

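### The metabolic substudy's baseline and end-test times, and study-pill use at the baseline test, are contradictory, so pre-post change in the OGTT and OFTT indices is ambiguously defined and may be attenuated

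*Protocol*

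**What the plan says.** **Baseline timing.** Protocol section 5.1 offers an optional metabolic substudy of an OGTT and an OFTT, run "on three admissions (at least 24 hours apart from each other"), with calorimetry. It places testing "on visits 2 (pretreatment) and 8 (4 weeks" post-treatment). Section 6 describes the first stage as "screening, enrollment, randomisation and baseline investigations (visits 1 and 2, over a maximum period of 14 days"), followed by 504 days of treatment over visits 3 to 7. Section 8.4 gives a different time for both tests. For the OFTT: "Within 3 months from entry, all patients will undergo a standard oral fat load test". For the glucose test: "Within 3 months from entry into the trial, patients will undergo a standard 75-g oral-glucose-tolerance test (OGTT").

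**Pills on test days.** In section 8, the paragraph on plasma curcumin and its metabolites says that on tolerance-test days "patients took two pills of their curcumin/placebo formulations together with the glucose or fat meal". It does not distinguish a baseline test from a later one.

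**End-test timing.** Section 5.1 describes visit 8 as 4 weeks after treatment. Section 6 has "visit 8, within 1 day of the EOT", and puts visit 9 at 12 weeks after EOT.

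**The concern.** A pre-post change needs a baseline free of treatment and an end test at a known time relative to the last dose. A site that follows section 5.1 obtains a pretreatment baseline. A site that follows section 8.4 may test patients who have taken their allocated product for weeks. If the pill rule in section 8 is applied at visit 2, the test is not free of treatment even there.

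The consequence is not symmetric between arms. A baseline measured on drug absorbs part of any effect in the curcumin arm and none in the placebo arm, so the between-arm difference in change shrinks. An end test 4 weeks off drug may also miss an effect that reverses. Section 9.2 adjusts continuous secondary outcomes for baseline. If that model were applied to these indices with a post-dose baseline, it would adjust for a variable that treatment had already altered, which does not repair the problem.

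What is at stake is the mechanistic evidence on glucose handling, insulin sensitivity and post-meal lipids. The primary histological outcome is not affected by the tolerance-test window or the pill rule.

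**Working it through.** **1. Reproduce the schedule (section 6).** 504 / 7 = 72 weeks of treatment. 84 / 7 = 12 weeks of follow-up. Visit 8 therefore falls at week 72 (to within 1 day) and visit 9 at week 84. The schedule has no visit at week 76, where section 5.1 would put visit 8.

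**2. Latest permitted baseline.** Take 3 months as 91 days (assumption).
- If entry is the start of dosing: 91 / 7 = 13 weeks on treatment, and 13 / 72 = 18% of the treatment period.
- If entry is the start of screening and all 14 days are used: (91 − 14) / 7 = 11 weeks on treatment, and 11 / 72 = 15%.

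**3. Pill rule at visit 2.** If pills are taken with the load there, only the time-0 sample at the first admission can precede any dose. Every post-load sample follows a dose. Because admissions are at least 24 hours apart, the second and third begin after a dose has already been taken. A test cannot be both pretreatment and taken with the allocated product.

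**4. End test.** It falls at week 72 under section 6, or at 72 + 4 = week 76 under section 5.1. Other visit labels do not settle the matter. The CKD regression definition in section 7 puts visits 7 and 8 three months apart, while the dietary and physical-activity paragraphs of section 8 call visit 7 end of treatment. Together those two would put visit 8 about three months after EOT, which agrees with neither section 5.1 nor section 6.

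**5. Interval between baseline and end test.**

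| Baseline | End test at week 72 | End test at week 76 |
|---|---|---|
| Week 0 | 72 weeks | 76 weeks |
| Week 11 | 61 weeks | 65 weeks |
| Week 13 | 59 weeks | 63 weeks |

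**6. Illustrative attenuation.** The protocol gives no onset or offset speed, so every figure here rests on an assumption.
- Linear onset: the effect at week t is E × t / 72, so a baseline at week b loses b / 72 of the week-72 effect. For b = 12, 12 / 72 = 16.7%. For b = 11 and b = 13 the losses are 15% and 18%.
- Exponential onset with half-time h: the effect is proportional to f(t) = 1 − 0.5^(t/h), and the share lost is f(13) / f(72). For h = 24, 12, 4 and 2 weeks the loss is about 36%, 54%, 89% and 99%.
- Exponential decline after the last dose: the share remaining 4 weeks off drug is 0.5^(4/h). For the same half-times it is 89%, 79%, 50% and 25%.

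**The case against.** The strongest counter-case is that the protocol states no analysis this could spoil. Section 7 lists no OGTT or OFTT index as an outcome, section 9.2 names no change-from-baseline analysis of them, and section 5.1 leaves a detailed summary of the substudy to a separate publication. This stands as a limit on importance. It does not cure conflicting instructions that sites must follow when collecting the data.

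Second, within 3 months of entry is an outer limit that a visit 2 test satisfies, and section 5.1 expressly calls visit 2 pretreatment. This is fair: an on-treatment baseline is permitted by section 8.4, not prescribed. Nor does the pill paragraph, which concerns kinetics, say that it applies at baseline; it only fails to exclude it. The grammar of section 5.1 also allows visits 2 and 8 to attach only to calorimetry. In that case no repeat tolerance test is scheduled and there is no change to measure, which is a further ambiguity and not a resolution.

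A reader might infer that change from baseline is uninterpretable, or that the whole treatment contrast is lost. The documents do not support either. If section 5.1 governs and the baseline is pill-free, change is well defined once the end time is fixed. Fasting indices from a time-0 sample taken before any pill would be unaffected. Total loss requires an effect complete by the late baseline, or one fully gone within 4 weeks off drug, and the protocol supports neither. Even then, a blinded randomised comparison of end-test values would not depend on the baseline.

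A reader might also infer that the listed glucose and lipid outcomes are compromised. They are fasting glucose, HbA1c and fasting lipids, with fasting samples collected at every visit, so the test window and the pill rule do not reach them. Finally, the reference to all patients in section 8.4 is weak evidence against an optional substudy, since it stands under the substudy heading.

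**Conclusion.** The point holds as an unresolved contradiction in three places: when the baseline tests are done, whether study pills are taken with them, and when the end test falls relative to EOT. Followed as written, the baseline may be up to about 11 to 13 weeks into treatment, the end test may be at week 72 or week 76, and the interval between them may run from 59 to 76 weeks. Any pre-post change in the OGTT and OFTT indices is therefore ambiguously defined and may be attenuated in the curcumin arm. The loss is about 17% for a week-12 baseline if onset is linear, and larger if onset is faster. These figures are illustrations, because the protocol gives no onset or offset speed.

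The reach is limited to optional mechanistic measures. A randomised end-test comparison remains valid whatever the baseline, although the visit 8 conflict leaves open whether it measures patients on or off drug. That conflict also extends beyond the substudy, because section 6 assigns the primary biopsy to visit 8.

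**What to change.** - Reconcile sections 5.1, 6, 8 (the plasma curcumin paragraph) and 8.4, together with the visit 7 and visit 8 labels in the CKD regression definition and the dietary and physical-activity paragraphs.
- Require the baseline OGTT and OFTT before the first dose and without study pills.
- State one end-test time relative to EOT and use it throughout.
- Analyse the pill-with-load kinetics separately from the baseline and change measures.
- Keep participants whose first test came after the first dose in the between-arm comparison of end-test values, without using that late test as a baseline. Dropping them altogether would be an avoidable post-randomisation exclusion in a trial planned for 52 patients.

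The cost is wording, plus one small analytical loss: participants tested late contribute no baseline-adjusted value.
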